10.1.2 Assessment of clinical endpoints

Patients are informed to contact center physicians in case an asymptomatic or symptomatic SARS-CoV-2 infections was diagnosed outside the settings of participating cohort centers. Clinical endpoints will be assessed at 4 weeks (±1 week), 8 weeks (±2 weeks) and 6 months (±4 weeks).

 Newly PCR-confirmed Covid-19 infection (identified by the presence of anti–SARS-CoV-2 nucleocapsid antibodies, or PCR or rapid antigen test)

During all visits at the trial centres (a PCR SARS-CoV-2 test will only be conducted if the treating physician would also conduct such a test during clinical routine (e.g. exposure to infected individual). PCR tests done in between independently will be recorded with dates and results. In case of a positive test result, physicians will check for symptoms and patients will be followed-up according to clinical routine and physicians' judgement.

• Newly PCR-confirmed symptomatic Covid-19 infection with at least one of the following symptoms (i.e. fever or chills, cough, shortness of breath or difficulty breathing, fatigue, muscle or body aches, headache, new loss of taste or smell, sore throat, congestion or runny nose nausea or vomiting, and diarrhea) at any time during the 48 weeks of follow-up

During all visits at the trial centres a PCR SARS-CoV-2 test will only be conducted if the treating physician would also conduct such a test during clinical routine (e.g. COVID-19 related symptoms; exposure to infected individual). In case of a positive test result, physicians will check for symptoms and patients will be followed-up according to clinical routine and physicians' judgement.

• Severe COVID-19 infection requiring hospitalization or leading to death

10.1.3 Assessment of safety outcomes

10.1.3.1 Vaccine specific adverse events

Patients will be asked at the 4 week study visit about the following specific vaccine related adverse events:

- Any symptoms at injection site (redness, swelling or pain) limiting continuation of normal daily activities during the first 7 days following the booster vaccination?
- Any systemic symptoms (fever, muscle pain, joint pain) limiting continuation of normal daily activities during the first 7 days following the booster vaccination?
- Any vaccine related symptoms leading to physician contact during the first 7 days following the booster vaccination?

10.1.3.2 Serious adverse events

Eventhough this is an observational study, we will systematically assess any serious adverse events that lead to hospitalization or death at 4 weeks, 8 weeks and 6 months follow up. Patients will be asked at these study visits about hospitalisations after having received the bivalent SARS-CoV-2 vaccines. In

addition, the information system from the hospital will be checked for information about hospitalisations or death of the patient.

10.1.3.3 Serious Events (SEs)

If a serious event occurs, the research project will be interrupted and the Ethics Committee notified on the circumstances via BASEC within 7 days according to HRO Art. 21.

The project is promptly notified (within 24 hours) if immediate safety and protective measures have to be taken during the conduct of the research project. The Ethics Committee will be notified via BASEC of these measures and of the circumstances necessitating them within 7 days.

A serious event is defined as any adverse event where it cannot be excluded, that the event is attributable to the sampling of biological material or the collection of health-related personal data, and which:

a. requires inpatient treatment not envisaged in the protocol or extends a current hospital stay;

b. results in permanent or significant incapacity or disability; or

c. is life-threatening or results in death.

10.1.3.4 Laboratory parameters

Laboratory parameters besides immune response parameters will be assessed at bi-annually cohort visits according to the cohort protocols.

10.1.3.5 Vital signs

Not relevant for purpose of this trial.

10.1.4 Assessments in participants who prematurely stop the study

All clinical outcomes will be assessed from routinely collected cohort data which will also be available if patients decide to prematurely stop participating in the clinical trial.

10.1.5 Assessments in participants who prematurely stop the study

We refer to the master protocol

10.1.6 Other assessments

In case a new SARS-CoV-2 vaccine shot will be recommended before the last 6 months follow-up visit is conducted we will add a case report form to assess the additional SARS-CoV-2 vaccines applied after the first bivalent mRNA vaccine shot.

11. PROCEDURES AT EACH VISIT

11.1.1 Eligibility

Potentially eligible patients will be either contacted ahead by cohort centres and informed about the substudy-3 and availability of bivalent vaccines or directly informed during cohort study visits. Eligibility of newly enrolled patients from STCS and SHCS will be prospectively assessed for eligibility based on the cohort stud- based trial platform. Treating physicians from the cohort centres will contact patients and inform them about the study. It will be mentioned that the new bivalent vaccines will be administered in the frame of clinical routine (as soon as the guidelines are adapted) and is not part of this study. In case they wish to receive the bivalent SARS-CoV-2 mRNA vaccine outside of this study, they have the option to participate in this observational study which only consists of additional blood samples being drawn and analysed to assess the immune response of the patient. It will be assessed which SARS-CoV-2 vaccines they received previously (i.e. first, second, and third vaccination). In case there are any reasons that justify to change to vaccine from different producers during their vaccination history this will be allowed following the judgment of the treating physician.

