4. BACKGROUND AND RATIONALE

4.1 BACKGROUND AND RATIONALE

We have set up a COrona VaccinE tRiAL pLatform (COVERALL) nested into the existing prospectively collected data structure of the Swiss HIV Cohort Study (SHCS) and the Swiss Transplant Cohort Study (STCS), according to an adaptive trial **master protocol** (4). Within the frame of a **first sub-study** we have assessed in a head-to-head comparison the efficacy of BNT162b2 by Pfizer-BioNTech and mRNA-1273 by Moderna in immunocompromised patients form the SHCS and the STCS (5). In these patients the antibody response of mRNA-1273 was non-inferior to BNT162b2. Patients living with HIV had in general an antibody response, while a high proportion of transplant recipients had no antibody response. The **second sub-study** found similar results 8 weeks after the 3rd vaccination (i.e. non-inferiority of moderna vaccine; antibody response; *manuscript in preparation*).

The currently used SARS-CoV-2 vaccines were developed targeting the SARS-CoV-2 wild type and show limited efficacy against newer SARS-CoV-2 variants of concern. Hence, Moderna has developed a new bivalent booster vaccine based on variant spike sequences (Wuhan/Omicron BA.1). In a recent study this newly developed bivalent mRNA-1273.214 vaccine showed also a potent neutralizing antibody response against Omicron subvariants and a superior antibody response against alpha, beta, gamma, delta and omicron variants when compared to the approved monovalent vaccine mRNA-1273 Spikevax (6). Similarly, Pfizer-BioNTech has developed a bivalent mRNA vaccine (Wuhan/Omicron BA.1) with promising results (7, 8). Currently, evidence on the efficacy and safety of bivalent mRNA-vaccines in immunocompromised persons is very limited.

Hence, we propose a **third sub-study** of our COVERALL study assessing the humoral and cellular immune response, clinical and safety outcomes of the bivalent mRNA-vaccines (Wuhan/Omicron BA.1) in patients from the SHCS and STCS who have received at least three monovalent m-RNA SARS-CoV-2 vaccinations by either Moderna or Pfizer-BioNTech. Little is known about the cellular (T-cell mediated) immune response for these bivalent vaccines. Evidence from previous mRNA vaccine studies has shown inconsistent patterns between humoral and cellular response, especially among solid organ transplant recipients (9-11).

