We propose to conduct an observational study, with two possible scenarios, dependent on how soon the second bivalent mRNA SARS-CoV-2 vaccine from Pfizer-BioNTEch will become available. Independently, we will start the study with the bivalent mRNA vaccine from Moderna which has already been approved by Swissmedic, being the first bivalent mRNA vaccine available in Switzerland. We will start a second observational arm with the bivalent mRNA vaccine from Pfizer-BioNTech, as soon as it has been approved by Swissmedic. This will allow a non-randomized comparison of the 2 bivalent mRNA vaccine s (Scenario 1 in Figure 1). In case the approval of Pfizer-BioNTech's bivalent mRNA vaccine comes later than than 3 months after study start, we will not open this second observational arm because the non-randomized comparability of the two arms will be too compromised due to time difference (Scenario 2 in Figure 1).

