7.6 ASSIGNMENT TO STUDY GROUPS

Since this is an observational study extension, we will not do any active assignment. Participants will receive the bivalent vaccine which they are given during routine practice. We will implement monitoring reports so capture how many patients from which sub-group are already participating. When the required sample size is reached for a specific sub-group investigators will be informed to stop recruitment for this sub-group of patients.

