11.1.2 Baseline assessment (before application of bivalent SARS-CoV-2 vaccination)

Patient will return the signed consent form which will also be signed by the treating physician. Patients will provide a blood sample of EDTA blood at the local study centre. After this they will go to the vaccination centre and receive the bivalent mRNA SARS-CoV-2 vaccine (either by Moderna or Pfizer-BioNTech) in the frame of clinical routine. Patients will also be asked about their previous vaccine history (i.e. which vaccines they received and when [months and year]) and if they have received monoclonal antibodies.

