13. STATISTICAL METHODS

Hypothesis

All analysese conducted will be of exploratory nature. For scenario 1, we expect to observe similar immunological outcomes for the two bivalent vaccines in our study population.

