13.3.2 Analyses of immunological and clinical outcomes

Descriptive statistics will be used to present immunological and safety outcomes. We will report frequency and percentage with 95% Wald confidene interval (CI) of positive immune response and

geometric mean titer (GMT) with 95% CI. GMT are defiened as the anit-logs of the means and addressed anticipated right-skewness of the data. Safety outcomes will be reported as frequency and percentage with 95% CI. For scenario 1, we will additionally report mean difference in positive response and ratio of GMT between the two bivalent vaccines with 95% CI.

Baseline and demographic characteristics will be summarised overall and -for scenario 1 – by vaccine received.

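### The Scenario 1 contrast takes no account of the producer of earlier doses, which may be associated with the bivalent product received

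*Protocol*

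**What the plan says.** All references are to the third sub-protocol (the document named Protocol).

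- **Aim.** In Scenario 1 the overall objective (section 6.1) is to compare the Moderna and Pfizer-BioNTech bivalent vaccines in immunocompromised patients.
- **How the product is chosen.** Section 7.6: "Participants will receive the bivalent vaccine which they are given during routine practice". There is no active assignment.
- **Timing.** Section 4.1: "we will start the study with the bivalent mRNA vaccine from Moderna which has already been approved by Swissmedic". The Pfizer-BioNTech arm opens on approval, and only if that comes within 3 months of study start.
- **Earlier doses.** Section 4.1 describes patients "who have received at least three monovalent m-RNA SARS-CoV-2 vaccinations by either Moderna or Pfizer-BioNTech". The exclusion criterion in section 7.4 asks only for basic immunisation and names two-dose courses of the two products as examples.
- **Changing producer.** Section 11.1.1: "In case there are any reasons that justify to change to vaccine from different producers during their vaccination history this will be allowed", subject to the treating physician's judgement.
- **Recording.** Section 11.1.2: "Patients will also be asked about their previous vaccine history (i.e. which vaccines they received and when [months and year", so product and date of earlier doses are both asked for.
- **Analysis.** Section 13.3.2: "For scenario 1, we will additionally report mean difference in positive response and ratio of GMT between the two bivalent vaccines with 95% CI". No covariate or stratum is named. Baseline characteristics are to be summarised by vaccine received, without saying which ones.
- **Status.** Section 13: "All analysese conducted will be of exploratory nature". The synopsis and section 4.1 call the comparison non-randomised. Section 7.2.3, on other methods of minimising bias, has no text.

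**The concern.** Every participant brings an earlier vaccine series to the study. If a change of producer needs a reason, patients with earlier Moderna doses will tend to appear in the Moderna bivalent arm, and patients with earlier Pfizer-BioNTech doses in the other. The endpoint is total anti-RBD antibody, which may still reflect the earlier doses. A difference between arms, or the similarity that section 13 expects, could then be credited to the bivalent product when part of it comes from the background series. This is separate from patient mix and calendar time: arms could match on both and still differ in vaccine history. The plan collects the information needed to examine this but does not use it in the contrast.

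**Working it through.** **The plan's own figure.** The Scenario 1 quotas in the synopsis sum as (30+30+50+50) + (10+10+30+30) = 160 + 80 = 240. This matches section 13.1, which calls it a convenience sample, so there is no power calculation to check.

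**Model for the bias.** Let *a* and *b* be the shares with earlier Moderna doses in the Moderna and Pfizer-BioNTech bivalent arms. Let *R* be the ratio of post-booster GMTs (earlier Moderna to earlier Pfizer-BioNTech) for the same bivalent dose, and *e* the corresponding difference in response proportion. Assume two background histories and no interaction with the bivalent product. Then:

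- crude GMT ratio = true ratio × R^(a−b)
- crude response difference = true difference + (a−b) × e

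**Cost of adjustment.** In a linear model with one binary covariate, adjusting for earlier producer inflates the variance by 1/(1−φ²). Here φ² = (a−b)² × p(1−p) / [m(1−m)], with p = 160/240 and m = p·a + (1−p)·b.

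The documents give none of *a*, *b*, *R* or *e*. All values below are assumptions.

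| a / b | a−b | GMT factor, R=1.25 | GMT factor, R=1.5 | Response bias, e=5 points | Variance inflation | Effective N |
|---|---|---|---|---|---|---|
| 50% / 50% | 0 | 1.00 | 1.00 | 0 | 1.0 | 240 |
| 70% / 30% | 0.4 | 1.09 | 1.18 | 2 points | 1.2 | 205 |
| 80% / 20% | 0.6 | 1.14 | 1.28 | 3 points | 1.5 | 160 |
| 90% / 10% | 0.8 | 1.20 | 1.38 | 4 points | 2.6 | 93 |
| 100% / 0% | 1.0 | 1.25 | 1.50 | 5 points | not separable | – |

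Worked line for 90%/10%:
- GMT factor: 1.25^0.8 = 1.20.
- m = (2/3)(0.9) + (1/3)(0.1) = 0.633.
- φ² = 0.64 × 0.222/0.232 = 0.612, so the inflation is 1/0.388 = 2.6.
- Cross-over cells: 16 of 160 in the Moderna arm and 8 of 80 in the Pfizer-BioNTech arm.

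**What the values mean.**
- With R = 1, or with a = b, there is no bias.
- The direction is unknown too: R below 1 pushes the ratio the other way.
- Only a−b matters for the bias. If the Moderna arm held 50% with earlier Moderna doses and the Pfizer-BioNTech arm 10%, the bias would be that of the 70%/30% row.
- For scale, if response were 90% in both arms (the first sub-protocol's planning assumption in its section 11.2, borrowed here only as an illustration), the crude Wald half-width is 1.96 × √[0.9 × 0.1 × (1/160 + 1/80)] = 8.1 points. That exceeds every response bias in the table.

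**The case against.** A reader might infer that the bivalent product is tied to the earlier producer, so that Scenario 1 compares whole vaccine sequences. The documents do not support that. Section 11.1.1 permits switching, and because its sentence follows one about the first three doses, it can be read as simply admitting mixed histories. Section 7.6 leaves the product to routine practice. Until the Pfizer-BioNTech product is approved, every participant receives Moderna's, whatever they had before, which works against a strict tie. Nor does section 7.4 confine earlier doses to these two producers, since its products are given as examples.

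Four further objections have weight:

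- **Status.** The comparison is exploratory and non-randomised, with no hypothesis test, and Scenario 2 has no contrast. This limits the consequence. It does not make an unadjusted contrast answer the stated aim, and the plan itself drops the second arm if the time gap would compromise comparability.
- **Sparse cells.** Adjustment is least informative where the association is strongest. This stands, and is why the adjusted estimate should sit beside the crude one.
- **Baseline titre.** It measures background antibody directly. However, section 13.3.2 does not use it either, and section 10.1.1 expects it to be missing in patients vaccinated before the study began.
- **A wider gap.** Earlier producer is one of several unadjusted factors. The quotas alone give transplant shares of 60/160 = 37.5% and 20/80 = 25%. This also stands, so patient group belongs in the same adjustment.

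The non-inferiority of mRNA-1273 reported from the earlier sub-studies (section 4.1) does not settle the matter, because it does not show R = 1.

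**Conclusion.** The point holds as a possibility that the analysis leaves unexamined. The bivalent product may be associated with the producer of earlier doses, and the recorded history is not used in the Scenario 1 contrast. The crude difference and GMT ratio can therefore mix the effect of the background series with that of the bivalent dose. The size is unknown and may be nil. On the assumed values, the factor on the GMT ratio runs from 1.00 (no association, or no effect of earlier product) to 1.38 (R = 1.5 with a 90%/10% split), and reaches the full effect of earlier product only under a complete tie, which no section states. These figures rest on a two-history model without interaction. The exploratory status keeps the weight moderate. The case for acting is that the change is cheap and lets readers judge whether the crude contrast can be taken at face value.

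**What to change.** Amend section 13.3.2 for Scenario 1 as follows:

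1. Tabulate by bivalent arm the producer of earlier doses (all Moderna, all Pfizer-BioNTech, mixed, other), the number of earlier doses and the months since the last dose. The number matters because sections 4.1 and 7.4 describe different minimum histories.
2. Keep the crude contrast. Beside it, report a difference in response and a GMT ratio, each with 95% CI, stratified by or adjusted for earlier producer, time since last dose and patient group.
3. State in advance that, if the cross-over cells are too sparse, the report will say that the contrast cannot separate the bivalent product from the earlier series.

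The cost is analysis text and one table, with no new visits or samples. The history questions in section 11.1.2 sit under the pre-vaccination baseline visit, so it is worth confirming that patients who consent after vaccination are asked them too. The statistical price is wider intervals: adjusting for earlier producer inflates the variance about 1.2-fold at a 70%/30% split and 2.6-fold at 90%/10%, both assumed.

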11.1.2 Baseline assessment (before application of bivalent SARS-CoV-2 vaccination)

Patient will return the signed consent form which will also be signed by the treating physician. Patients will provide a blood sample of EDTA blood at the local study centre. After this they will go to the vaccination centre and receive the bivalent mRNA SARS-CoV-2 vaccine (either by Moderna or Pfizer-BioNTech) in the frame of clinical routine. Patients will also be asked about their previous vaccine history (i.e. which vaccines they received and when [months and year]) and if they have received monoclonal antibodies.

11.1.3 Study specific follow-up

4 weeks, 8 weeks and 6 months: Patients will be asked about SARS-CoV-2 infections and about adverse events. Further, patients will provide a blood sample of EDTA blood to assess the immunological outcomes. During all study visits patients will be asked if they received monoclonal antibodies.

Sub sample of patients for T-Cell tests (baseline, 4 weeks and 6 months): Patients will provide at least 8ml heparin blood which is immediately transferred to the IMV in Zürich for processing on the same day.

12. SAFETY

The PI (and if applicable the sponsor) is promptly notified (within 24 hours) if immediate safety and protective measures have to be taken during the conduct of the research project. The Ethics Committee will be notified via BASEC of these measures and of the circumstances necessitating them within 7 days.

13. STATISTICAL METHODS

Hypothesis

All analysese conducted will be of exploratory nature. For scenario 1, we expect to observe similar immunological outcomes for the two bivalent vaccines in our study population.

13.1 DETERMINATION OF SAMPLE SIZE

Not applicable. The present study does not aim to test an hypothesis and a convenience sample of 240 participants for scenario 1 and 160 for scenario 2 has been chosen to better understand immunological response to bivalent vaccines in an immunocompromised population.

13.2 STATISTICAL CRITERIA OF TERMINATION OF TRIAL

Not applicable. No interim analysis is planned during the trial extension and termination will not be based on any statistical criteria.

13.3 PLANNED ANALYSES

13.3.1 Datasets to be analysed, analysis populations

We refer to the master protocol

13.3.2 Analyses of immunological and clinical outcomes

Descriptive statistics will be used to present immunological and safety outcomes. We will report frequency and percentage with 95% Wald confidene interval (CI) of positive immune response and

geometric mean titer (GMT) with 95% CI. GMT are defiened as the anit-logs of the means and addressed anticipated right-skewness of the data. Safety outcomes will be reported as frequency and percentage with 95% CI. For scenario 1, we will additionally report mean difference in positive response and ratio of GMT between the two bivalent vaccines with 95% CI.

Baseline and demographic characteristics will be summarised overall and -for scenario 1 – by vaccine received.

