6.4 STUDY OUTCOMES

6.4.1 Immunological Outcomes

Immunological endpoints:

- The proportion of patients with a positive antibody response to SARS-CoV-2 spike (S1) protein receptor binding domain in human serum or plasma assessed by the commercial immunoassay Elecsys Anti-SARS-CoV-2 S (Elecsys S) from Roche(1) 4 weeks, 8 weeks, and 6 months after vaccination. An antibody response will be considered to be still sufficient, using the threshold ≥100 units/ml, predicting a protective immune response as indicated by Hall et al.(2), and Khoury and colleagues.(3)
- Geometric mean of quantitative antibodies against RBD at 4 weeks, 8 weeks, and 6 months using Elecsys S test from Roche.
- The proportion of patients with a positive antibody response using SARS-CoV-2 spike (S1) Elecsys S by Roche, using a threshold of ≥0.8 units/ml as defined by the manufacturer at 4 weeks, 8 weeks, and 6 months.
- T-Cell response, using a commercially available IFN-γ release assay (Quant-T-Cell SARS-CoV-2 by Euroimmun and Elecsys® IGRA SARS-CoV-2 by Roche) in a subsample of 60 patients (40 receiving bivalent (Wuhan/BA.1) SARS-CoV-2 mRNA-1273.214 vaccine by Moderna; 20 receiving bivalent (Wuhan/BA.1) SARS-CoV-2 mRNA vaccine by Pfizer-BioNTech) 4 weeks and 6 months after vaccination (sub-sample will be decreased to 40 patients in Scenario 2).

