13.3.4 Safety analysis

Safety issue is expected to be small and will be describe using number, frequency and 95% CI.

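### The Wald interval named for response proportions in sub-study 3 breaks down if response nears 100%, as is plausible for people with HIV at 0.8 units/ml; Wilson or Clopper-Pearson would avoid this

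*Protocol*

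**What the plan says.** Protocol (third sub-protocol), section 13.3.2, plans to report "frequency and percentage with 95% Wald confidene interval (CI) of positive immune response". It offers no other method for proportions close to 0% or 100%. For Scenario 1, "we will additionally report mean difference in positive response and ratio of GMT between the two bivalent vaccines with 95% CI", and for safety (13.3.4), "Safety issue is expected to be small and will be describe using number, frequency and 95% CI". Neither of these names an interval method.

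Section 6.4.1 defines positivity at two cut-offs, 100 units/ml and a much lower one, "using a threshold of ≥0.8 units/ml as defined by the manufacturer at 4 weeks, 8 weeks, and 6 months". No expected response rate is given for sub-study 3. The nearest statement is in section 4.1, on earlier doses: "Patients living with HIV had in general an antibody response, while a high proportion of transplant recipients had no antibody response".

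The Study Synopsis sets the planned numbers:

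- Moderna arm (160): 50 + 50 people with HIV in two CD4 strata, 30 + 30 transplant recipients.
- Pfizer-BioNTech arm (80, Scenario 1 only): 30 + 30 people with HIV, 10 + 10 transplant recipients.

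Section 7.6 uses these groups as recruitment quotas ("When the required sample size is reached for a specific sub-group investigators will be informed to stop recruitment"). Section 13.3.2 does not say whether response will be reported by patient group or by stratum.

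**The concern.** The Wald interval estimates its standard error from the observed proportion. As that proportion nears 100% the estimated error shrinks towards zero while the true uncertainty does not. Three things follow. Coverage can fall well below 95%, the upper limit can pass 100%, and if everyone responds the interval is a single point.

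Response near 100% is plausible in part of this study. People with HIV are the majority of each arm, are described as generally responding, must already have had basic immunisation (section 7.4), then receive a further dose, and are scored at the manufacturer's low cut-off. It is less assured at 100 units/ml, especially at 6 months.

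The study tests no hypothesis and uses a convenience sample (section 13.1), so the estimates and their intervals are its result. A line such as 100% (100 to 100) from 30 to 100 patients would claim a certainty the data cannot give.

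**Working it through.** Sub-study 3 states no interval, power or calculated sample size, so there is no figure of its own to reproduce first. The response rates below are assumptions; the group sizes come from the Study Synopsis.

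**Formulas**

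- Wald: p̂ ± 1.96·√(p̂(1−p̂)/n).
- Exact coverage at true rate p: the sum over x = 0…n of the binomial probability of x, counting only those x whose interval contains p.
- Zero width at 100%: every participant responds, probability pⁿ.
- Upper limit above 100%: with k ≥ 1 non-responders this occurs when k < 3.84·(1 − k/n). For n of 30 or more that means k = 1, 2 or 3.

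**One case in full: n=60, p=0.98**

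- 60/60 has probability 0.98⁶⁰ = 0.298. The interval is 100 to 100% and misses 98%.
- 54/60 has an upper limit of 97.6%, so 54 or fewer responders also miss; their probability is about 0.001.
- Coverage = 1 − 0.298 − 0.001 = 0.701.
- Upper limit above 100%: 57, 58 or 59 responders, 0.0865 + 0.2194 + 0.3644 = 0.670.

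**People with HIV, same method**

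| n | Wald coverage at 90 / 95 / 98% | Wilson coverage at 98% | Upper limit >100% at 98% | Zero width at 98% |
|---|---|---|---|---|
| 100 (both strata, Moderna) | 93.2 / 87.7 / 86.6% | 94.9% | 73% | 13% |
| 60 (both strata, Pfizer-BioNTech) | 94.1 / 80.6 / 70.1% | 96.8% | 67% | 30% |
| 50 (one stratum) | 87.9 / 92.0 / 63.5% | 92.2% | 62% | 36% |
| 30 (one stratum) | 80.9 / 78.2 / 45.4% | 97.8% | 45% | 55% |

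Over all twelve combinations of n and rate, Wilson coverage lies between 92% and 98%. At more extreme rates Wilson also dips (86.0% at n=30 and 99.5% response), while Clopper-Pearson stays above 95% (99.0% in that case).

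**What would be printed**

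| Result | Wald | Clopper-Pearson |
|---|---|---|
| 59/60 | 95.1 to 101.6% | 91.1 to 100.0% |
| 49/50 | 94.1 to 101.9% | 89.4 to 99.9% |
| 60/60 | 100 to 100% | 94.0 to 100% |
| 30/30 | 100 to 100% | 88.4 to 100% |

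**Whole arms**

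Here the response count is the sum of two independent binomials, with HIV response set at 98%. The arm's true rate is the weighted mean, for example (60×0.98 + 20×0.80)/80 = 93.5%.

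| Transplant response | Moderna arm, n=160: Wald coverage | Pfizer-BioNTech arm, n=80: Wald coverage | n=80: upper limit >100% |
|---|---|---|---|
| 60% | 96.5% | 97.6% | 0.6% |
| 80% | 94.5% | 90.8% | 21.0% |
| 90% | 90.4% | 83.5% | 56.5% |

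**Safety, if Wald were carried over** (the plan does not say so): with no events in 80 patients Wald gives 0 to 0%, while the exact upper limit is 4.5%. At an assumed event rate of 1%, coverage is 55% at n=80 and 80% at n=160.

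**The case against.** The strongest counter-argument is that the worst figures belong to analyses the plan does not state. Section 13.3.2 promises no response proportion by HIV status or CD4 stratum, and the groups of 50 and 30 are recruitment quotas. For whole arms, the protocol's own remark that many transplant recipients did not respond points towards rates where Wald behaves well, as the 60% row shows. The 98% rate is assumed. Half of the planned HIV sample has CD4 below 350, which the Study Synopsis itself places at higher risk of a low immune response. At 90% response the HIV groups of 100 and 60 cover 93.2% and 94.1%. Finally, section 13 says "All analysese conducted will be of exploratory nature", and because counts are reported with percentages, a reader can compute another interval.

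Much of this stands. It makes the problem conditional and limits its weight. It does not remove it: reporting each vaccine arm as a whole is what Scenario 1 needs, and the 80-patient arm under-covers once transplant response reaches about 80%. Readers should not have to recompute intervals.

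The master protocol, which is not among the documents, might hold a general rule. But 13.3.2 names Wald itself and does not defer to the master protocol, unlike 13.3.1, 13.3.5 and 13.4.

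It is also fair that Wald is not prescribed for safety or for the Scenario 1 difference. Those are missing details, not errors.

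**Conclusion.** The concern holds, in conditional form. The plan fixes an interval method that fails in a range of response rates this study could well meet, and provides no fallback. The failure is large for people with HIV if their response is about 98% and they are reported separately (coverage 86.6% at n=100, 70.1% at n=60, lower by stratum). It is moderate for the whole Pfizer-BioNTech arm if transplant response is 80% to 90%, and absent for whole arms if transplant response is about 60%. These sizes rest on assumed response rates, and the HIV figures also on reporting by patient group or stratum.

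The practical consequence is modest. No decision rule uses these intervals, and the geometric mean titre intervals are unaffected. The change is worth making because it costs almost nothing and avoids limits above 100% or of zero width in the published tables.

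**What to change.** In section 13.3.2, replace Wald with Wilson or Clopper-Pearson for all response proportions, at both cut-offs and all visits. Clopper-Pearson is the choice if coverage of at least 95% is wanted throughout; Wilson gives narrower intervals.

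Three clarifications can be made in the same edit, though the main point does not depend on them:

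- Name the same method for the safety percentages in 13.3.2 and 13.3.4.
- Name a Newcombe or Miettinen-Nurminen interval for the Scenario 1 difference. A Wald interval for the difference would also have zero width if everyone in both arms responded.
- State whether response will be reported by patient group, by recruitment stratum or only by vaccine.

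The cost is one word changed, two methods named and a different function call. Intervals near 0% or 100% become slightly wider. Sample size, visits and data collection are unchanged.
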